Study Design: Basic experimental study in humans, single-blinded, cross-over

Number of subjects: up to 60 (to achieve 40 analyzable subjects)

Description of Intervention: Basic Experimental Studies with Humans (BESH)

Estimated Time to Complete Enrollment: 2 years

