4.0 Study Participants

4.1 Participants inclusion/exclusion criteria

Participants will be healthy individuals, ages 18-50. The upper limit of 50 will reduce variance from older subjects, who exhibit less specific activation patterns.(63, 64) We will recruit ~60 individuals (50% women) to allow for drop-outs and subjects who cannot tolerate TBS, aiming for 40 subjects in the final analysis.

Inclusion/exclusion criteria: (1) No history of past or current mental illness (except for simple phobias), but prior h/o substance dependence OK if in remission for greater than 5 years; (2) Not taking any medication, prescription or non-prescription, with psychotropic effects (birth control medications allowed); (3) No first-degree family members with a history of epilepsy; (4) Age 18 –50; (5) If a woman of child bearing age, not pregnant or trying to become pregnant; (6) No history of serious neurological illness (including, but not limited to, seizures/epilepsy) or current medical condition that could compromise brain function, such as liver failure; (7) No history of closed head injury, e. g. loss of consciousness > ~5 min, hospitalization, neurological sequela; (8) Ability to tolerate small, enclosed spaces without anxiety; (9) No family history of epilepsy in first degree relatives; (10) No metals, implants or metallic substances within or on the body that might cause adverse effects to the subject in a strong magnetic field, or interfere with image acquisition, e. g. aneurysm clips, retained particles (e.g. metal workers with exposures), neurostimulators, foil-backed transdermal patches, carotid or cerebral stents, CSF shunts; magnetic dental implants, ferromagnetic ocular implants, pacemakers, automatic implantable defibrillators; (11) Size compatible with scanner gantry, e. g. men over 6 feet tall that weigh more than 250 lbs, men under 6 feet tall that weigh over 220 lbs, women over 5'11" tall that weigh more than 220 lbs, or women under 5'10" tall that weigh more than 200 lbs. Subjects of these weights or greater typically have difficult fitting into the fMRI scanner properly; (12) Ability and willingness to give informed consent to participate.

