6.5 Participant discontinuation/withdraw

During the pre-screening process, subjects who are found to be non-eligible, before signing the consent form, will be considered *not enrolled*, and all data related to that subject will be destroyed. Subjects who consent, and are found not eligible during the assessment and screening will be considered *screen failures*, and all research and identifying data will be destroyed, except for the consent form and limited information to document the screen failure (age, gender, diagnosis, specific reason for exclusion). Subjects will receive a subject number at the time of consenting. Subjects who pass screening will be considered *enrolled*. Subjects who leave the study after signing the informed consent, and after being deemed eligible/enrolled/randomized, will be considered *withdrawn*. Subjects may withdraw from the study at any time and for any reason. Subjects may be withdrawn by the investigator when continued participation would present an unacceptable risk to the subject. Based on previous experience, we expect that most subjects will be compliant with the study protocol.

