Analysis plan: For analysis of n-back performance, our primary performance measure will be accuracy to the 2-back condition. Secondary measures will be d-prime, to capture the sensitivity to the target and not bias to respond, and median reaction time. Although we found significant effects on d-prime for our list learning paradigm, that memory task was very different from the more demanding n-back, which requires updating and manipulation in short-term storage, while our list learning task involved only incidental memory. For each measure, we will conduct a repeated measures ANCOVA, with the performance measure across the three iTBS conditions as the repeated measure, and sex as a fixed, between-subject factor and age as a co-variate. Post-hoc, paired t-tests will be used for specific contrasts.

(H3.1) 2-back accuracy will be greater for dlPFC stimulation (no task during iTBS) relative to vertex stimulation

(H3.2) 2-back accuracy will be greater for dlPFC stimulation applied while subjects carry out an n-back during iTBS stimulation during stimulation, compared to when they receive stimulation alone. The same hypotheses will be applied to d-prime, our secondary measure. Two-sided tests will be used, because it is also possible that performance may worsen, either with stimulation alone, or when combined with subjects performing the n-back. It would be critical to know, for example, that performance of a cognitive control task was degraded by combining TMS with a task. Although a commercial device is being tested on dementia patients, relying on the assumption that the combination is beneficial,(18) we are not aware of this assumption being tested as we propose to do here.

Exploratory analyses around performance correlations: In addition to testing questions about performance, we will also examine correlations between performance and the MRI measures from Aims 1 and 2, testing important questions around mechanism. Since we will systematically test for correlations between both performance measures and the three primary measures from each aim (18 correlations), alpha will be set at $0.05/18 = 0.0028$.

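### The Aim 3 repeated measures ANCOVA by default drops anyone missing one of the three iTBS sessions, and the plan does not say which subjects enter the paired t-tests; a mixed model on all sessions is a cheap, modest improvement

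*Combined protocol and SAP*

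**What the plan says.** Section 8.0, Specific Aim 3, sets one model for each performance measure: "we will conduct a repeated measures ANCOVA, with the performance measure across the three iTBS conditions as the repeated measure". Sex is a between-subject factor and age a covariate. The next sentence adds: "Post-hoc, paired t-tests will be used for specific contrasts".

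Each Aim 3 hypothesis involves only two of the three conditions:
- H3.1: "2-back accuracy will be greater for dlPFC stimulation (no task during iTBS) relative to vertex stimulation".
- H3.2: accuracy is greater for "dlPFC stimulation applied while subjects carry out an n-back during iTBS stimulation during stimulation, compared to when they receive stimulation alone".

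Tests are two-sided: "Two-sided tests will be used, because it is also possible that performance may worsen". No alpha is given for these tests.

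The study summary gives the number of subjects as "up to 60 (to achieve 40 analyzable subjects"). Section 4.1 says the surplus is "to allow for drop-outs and subjects who cannot tolerate TBS, aiming for 40 subjects in the final analysis". Section 6.5 adds: "Subjects may withdraw from the study at any time and for any reason". Section 4.4 counterbalances the three sessions over Visits 3, 4 and 5.

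No section says how a missing session is handled in the Aim 3 analysis. Section 7.2 treats missed assessments only as a matter of deviation reporting. The 60% frame cutoff in section 8.0 concerns motion in the resting-state scans.

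**The concern.** A classical repeated measures ANCOVA over three conditions keeps only subjects with all three values. That is a property of the method; the protocol does not prescribe deletion. A subject who completes two stimulation sessions and then leaves would drop out of the main Aim 3 model, although the two sessions held are often exactly the pair that one hypothesis needs.

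Three things are at stake:
- Some precision is lost.
- The ANCOVA result is conditional on having completed all three sessions.
- The analysis set for the paired t-tests is undefined. If they use all available pairs, the ANCOVA and its follow-up tests rest on different subjects. If they use completers only, usable pairs are discarded. The plan leaves this choice open until the data are seen.

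**Working it through.** **The plan's own figure.** 40 / (1 - 1/3) = 60, but the one-third is itself 1 - 40/60, so this check is circular. The documents give no effect size, SD, power or drop-out rate, so the target of 40 cannot be reproduced. The number of subjects who will stop after exactly two sessions, k, is not given either. It is treated below as an assumption over a range.

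**Which pair does a two-session subject hold?** Write V for vertex, D for dlPFC at rest and DT for dlPFC with the n-back. The first two sessions in the six possible orders are:
- V, D or D, V: the H3.1 pair (2 of 6).
- D, DT or DT, D: the H3.2 pair (2 of 6).
- V, DT or DT, V: neither pair (2 of 6).

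So 4/6 = 2/3 hold a complete pair for one hypothesis. Either three-order Latin square gives the same 2/3. This assumes that withdrawal is unrelated to order. The remaining third still informs both contrasts indirectly in a mixed model.

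**Precision.** Take 40 completers plus k two-session subjects spread equally over the three pairs, with equal within-subject correlation r (compound symmetry) and no visit term. The variance of a pairwise contrast is 2(1 - r)s² / N_eff, where s² is the variance of a single measurement and N_eff is:
- completers only: 40
- paired t-test on all available pairs: 40 + k/3
- mixed model: 40 + (k/3)(2 + r)/(1 + r)

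Example with k = 12 and r = 0.5: the mixed model has N_eff = 40 + 4 × 2.5/1.5 = 46.7. Against completers, 1 - 40/46.7 = 14.3%. Against available pairs, 1 - 44/46.7 = 5.7%.

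| k (assumed) | Available pairs | Mixed-model N_eff, r = 0.5 / 0.7 | Variance cut vs completers, r = 0.5 / 0.7 | Variance cut vs available pairs, r = 0.5 / 0.7 |
|---|---|---|---|---|
| 1 | 40.3 | 40.6 / 40.5 | 1.4% / 1.3% | 0.5% / 0.5% |
| 2 | 40.7 | 41.1 / 41.1 | 2.7% / 2.6% | 1.1% / 1.0% |
| 3 | 41 | 41.7 / 41.6 | 4.0% / 3.8% | 1.6% / 1.4% |
| 6 | 42 | 43.3 / 43.2 | 7.7% / 7.4% | 3.1% / 2.7% |
| 9 | 43 | 45.0 / 44.8 | 11.1% / 10.6% | 4.4% / 3.9% |
| 12 | 44 | 46.7 / 46.4 | 14.3% / 13.7% | 5.7% / 5.1% |

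**Power.** Assume a standardised paired effect of 0.45 and a two-sided alpha of 0.05; neither is in the documents. Power is 79.3% with 40 completers. With k = 3 it is 80.3% on available pairs and 80.9% with the mixed model (r = 0.5). With k = 12 it is 83.1% and 85.3%.

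**The case against.** The strongest reply is that H3.1 and H3.2 are tested by paired t-tests, each of which needs only its own two sessions. If those tests use all available pairs, little is lost for the hypotheses themselves. This stands. The loss is certain only for the ANCOVA, and the fair comparator for the contrasts is the last column of the table. What does not go away is that the plan never states which subjects the paired tests use.

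Second, k is probably small. Subjects who cannot tolerate iTBS leave at the Visit 2 trial run (section 6.2.3.2), before any experimental condition. The three sessions are 1 to about 4 days apart, preferably within one week. Section 6.5 expects most subjects to comply. The surplus of 20 covers intolerance and drop-out together, so it is no evidence for values of k near 12. This also stands, and it is why the rows for k = 1 and 2 are shown.

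Third, recruiting up to 60 protects the number analysed. It does protect the count, but it neither recovers discarded sessions nor removes the selection on completing all three visits.

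Fourth, section 8.0 allows small departures in implementation. That is a reason to fix the missing-session rule in advance, since the choice of analysis set would otherwise fall within that latitude.

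**Conclusion.** The point holds as a modest improvement. The Aim 3 ANCOVA by default excludes subjects with a missing session, drop-out is foreseen, and the analysis set for the paired contrasts is unstated. With 3 to 12 two-session subjects, a mixed model gains about 4-14% in variance over completers only and about 1.4-5.7% over available pairs. With 1 or 2 such subjects it gains about 1-3% and 0.5-1.1%. These figures rest on assumed k, 40 completers, correlation 0.5-0.7, compound symmetry, withdrawal unrelated to order, and no visit term.

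Three stronger readings are tempting but not supported:
- A reader might infer that the plan throws away the evidence for H3.1 and H3.2. It does not say so, and the paired t-tests may use every available pair.
- A reader might infer that scan data are lost. The Aim 3 model analyses n-back performance, and the imaging hypotheses H1.x and H2.x already compare two sessions each.
- A reader might infer that Aim 3 will run on well under 40 subjects. If, say, 6 of the 40 lacked a session, the ANCOVA would keep 34. But the term analyzable is not defined for Aim 3, and recruitment of up to 60 is meant to deliver 40.

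The documents also give no evidence that completers differ from withdrawals, so bias is a possibility and not a finding.

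**What to change.** Replace the repeated measures ANCOVA, for accuracy and for the secondary performance measures, with a linear mixed model:
- fixed effects for condition and visit (period), with the same sex and age terms;
- a random intercept for subject;
- all available sessions from Visits 3-5.

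Read H3.1 and H3.2 as two contrasts of this model and report N for each. The visit term matters because a subject who stops after two sessions always lacks the last visit, which upsets the counterbalance, and because the n-back is repeated, so practice effects are possible. The gains above were not recomputed with this term.

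Define an analyzable subject for Aim 3. If paired t-tests are kept alongside the model, state that they use every subject with both sessions. For H1.x and H2.x, one clarifying sentence to the same effect is enough.

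The cost is wording only, with no added visits or enrolment. The downsides are that N will differ between contrasts, and that the model assumes withdrawal is ignorable given the observed data. The indirect gain also relies on equal within-subject correlation across conditions, which a paired t-test does not need.

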4.4 Intervention assignment procedures

All subjects will receive all interventions in a cross-over design. The three intervention sessions (visits 3, 4 & 5) will be given in counter-balanced order, stratified by gender. Subjects will be blind to the nature of the questions being asked; however, they will be told that different stimulation paradigms will be used, which will be evident to the subjects as they go through the procedures.

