6.2.3.1 Motor threshold: Motor threshold will be obtained to calibrate the intensity of stimulation delivered for the TBS TMS sessions. Motor evoked potentials (MEPs) elicited using biphasic posterior-anterior stimulation will be recorded from right first dorsal interosseous (FDI) using surface electromyography (Rogue Research, Montreal, Canada). The motor cortical hotspot will be defined as the site of stimulation in left motor cortex that elicits the largest, consistent response in the FDI with the coil oriented at 45 degrees to the coronal plane. Active motor threshold (AMT) will be obtained as the percentage of stimulator output that elicits an MEP of $\geq 200 \mu\text{V}$ peak-to-peak on ten out of twenty trials while the subject is contracting the FDI muscle at approximately 20% of their maximum.(77)

6.2.3.2 Trial run of iTBS: In order to see if subjects can tolerate iTBS, we will do a 2-3 minute run of iTBS to the dorsolateral prefrontal cortex (approximate location). If a subject cannot tolerate iTBS, they will be withdrawn from the protocol (but receive payment for the 2 visits they completed).

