6.3.3 TMS session: We will deliver iTBS, which has been shown to increase cortical excitability,(30) using 3 pulses of stimulation at 50 Hz, repeated every 200 ms, for 2 sec trains, repeated every 10 sec, giving a total of 600 pulses in 190 sec. Stimulation will be delivered at 80% of AMT, which is within consensus recommendations for safety,(80) and used in published work.(81)

In counter-balanced order, subjects will receive one of three iTBS sessions on each of the 3 days: 1) Vertex stimulation and subjects will be instructed to maintain gaze on a fixation screen and rest; 2) dlPFC stimulation (from neuronavigated target described above, subjects will be instructed to maintain gaze on a fixation screen and rest; or 3) dlPFC stimulation augmented with an n-back task. A computer screen will display an n-back task, using the 2-back condition. Letters will appear for 0.5 sec every 2 seconds, and presentation will be synchronized with the iTBS stimulation, which will occur 0.5 sec before the onset of every 5th letter. Actual parameters may differ slightly when delivered in the experiment.

6.3.4 MRI session: MRI sessions will be identical to Visit #2. The MRI will follow immediately after the iTBS TMS session.

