Exploratory analysis, amplitude of low frequency fluctuations (ALFF): ALFF, and fractional ALFF (fALFF), measures the magnitude of low frequency BOLD fluctuations, generally from 0.01 to 0.1 Hz.(99) fALFF measures the fractional strength (relative to the full spectrum) of BOLD fluctuations. ALFF is correlated with CBF,(100, 101) so this measure provides an alternative to supplement the pCASL analysis. This is a potentially important measure for brain stimulation, as fALFF/ALFF abnormalities have been reported in psychiatric disorders,(102-104) and fALFF in the subgenual cingulate gyrus has been shown to predict response to electroconvulsive therapy.(105) This analysis will use the BOLD resting data as above, except that frame censoring (scrubbing) will not be performed, since censoring can affect the frequencies in a run of BOLD-acquired MRI data. Each voxel's BOLD time series will be transformed into the frequency domain and the mean amplitude of the spectrum over the frequency range of 0.01–0.1 Hz will determine ALFF. fALFF for two bands (slow-4; 0.027-0.073 Hz; and slow-5, 0.01-0.027 Hz) will be calculated as the magnitude for that band over the magnitude of the full spectrum. This analysis will focus on the 10 mm diameter sphere under the site of stimulation. Alpha level for this analysis will be set at 0.017 (0.05/3), two-tailed.

Exploratory analyses, between measures: Exploratory analyses will also test for correlations between the three MRI measures, to provide a richer picture of iTBS effects. Lastly, we recognize that vertex stimulation, here being used as a control condition for dlPFC stimulation, may have some effects on brain networks, although it was selected to avoid the FPN. With some caveats (effect of order, since baseline is not counter-balanced), we can use baseline measures from the first MRI session (no preceding TMS session), to see if iTBS differences represent a change in the dlPFC-stimulated condition or the vertex-stimulated condition. An additional exploratory analysis will compare stimulation over the 'activated target' (2-back minus 1-back) versus the 'deactivated target' (1-back minus 2-back), based on how the target was selected.

Specific Aim 2: Demonstrate modulation of the effect of dlPFC iTBS by a cognitive task

Primary outcome measures:

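### Aim 3 (H3.1, H3.2): visit position is counterbalanced but not modelled, so the tests are valid but lose some power if 2-back accuracy drifts over visits 3 to 5

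*Combined protocol and SAP*

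**What the plan says.** Section 4.4 says that the intervention sessions at visits 3, 4 and 5 "will be given in counter-balanced order, stratified by gender", and Section 6.3.3 repeats this: "In counter-balanced order, subjects will receive one of three iTBS sessions on each of the 3 days". The number of orders used (three or six) is not given. Section 6.3.4 adds that "MRI sessions will be identical to Visit #2", so every subject does the same n-back scan at baseline and after each stimulation session.

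For Aim 3, Section 8.0 takes 2-back accuracy as primary, with d-prime and reaction time as secondary. Each goes into a repeated measures ANCOVA over the three conditions, with "sex as a fixed, between-subject factor and age as a co-variate. Post-hoc, paired t-tests will be used for specific contrasts". Tests are two-sided. No alpha, SD, effect size or power is stated for H3.1 or H3.2.

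The analysis section mentions order once, as a caveat on an exploratory comparison: "With some caveats (effect of order, since baseline is not counter-balanced), we can use baseline measures from the first MRI session".

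**The concern.** The design controls visit order, but the Aim 3 analysis does not use that control. Sex and age are constant within a subject, so they cannot absorb a change from visit to visit. If subjects improve with practice, a condition that falls later gains from its position. Over balanced orders these gains cancel in the mean difference, but they spread the individual differences apart. The paired t-test counts that spread as random error.

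What is at stake is sensitivity. With a trend, the confidence interval is wider than it need be and a real difference is missed more often. That includes the harm the plan most wants to detect: "It would be critical to know, for example, that performance of a cognitive control task was degraded by combining TMS with a task".

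A lesser issue is that balance among those analysed will not be exact. Forty is not a multiple of 3 or 6, and Section 4.1 recruits about 60 "to allow for drop-outs and subjects who cannot tolerate TBS, aiming for 40 subjects in the final analysis". Some of any trend could then remain in the estimate by chance.

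**Working it through.** The plan has no figure of its own to reproduce here.

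**From the documents.** 40 analysed of about 60 recruited (Section 4.1); three conditions counterbalanced over three visits (Sections 4.4 and 6.3.3); two-sided paired t-tests (Section 8.0).

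**Assumed.** Alpha 0.05. The SD of the within-subject difference, apart from visit effects, is set to 1. The true effect is 0.454 SD, which gives 80% power with 40 subjects and no trend. There is a common gain of k SDs per visit. For scale only: if that SD were 5 to 10 accuracy points, k = 0.3 would be 1.5 to 3 points per visit.

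**Step 1, variance.** Over six balanced orders the visit-position difference between two conditions is -2, -1, -1, +1, +1, +2. Its mean is 0 and its mean square is (4+1+1+1+1+4)/6 = 2. The estimate is therefore unbiased with true variance 1/40, while the paired t-test estimates about (1 + 2k²)/40. Its standard error is too large by √(1 + 2k²). If learning stops after visit 4 (gains 0, k, k), the mean square is 4/6 of k² and the factor is √(1 + 2k²/3).

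**Step 2, power by approximation.** The standardised effect is 0.454 × √40 = 2.871 and the critical t on 39 df is 2.023. Power is about Φ(2.871 − 2.023 × factor):
- k = 0: Φ(0.848) = 80%
- k = 0.2: factor √1.08 = 1.039, Φ(0.769) = 78%
- k = 0.3: factor √1.18 = 1.086, Φ(0.674) = 75%
- k = 0.5: factor √1.50 = 1.225, Φ(0.393) = 65%

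**Step 3, simulation** (20,000 runs per cell, 6 or 7 subjects per order). The paired t-test on 39 df is compared with the difference adjusted for categorical visit on 37 df. Ranges span repeat simulations.

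| k | Power, paired t, linear | Power, adjusted, linear | Null rejection, paired t, linear | Power, paired t / adjusted, plateau |
|---|---|---|---|---|
| 0 | 80% | 80% | about 5% | – |
| 0.2 | 77–78% | 80% | 4.1–4.3% | 79.6 / 80.1% |
| 0.3 | 75% | 80% | 3.2–3.7% | 78.5 / 79.9% |
| 0.5 | 65% | 80% | 1.5–2.0% | 74.8 / 79.6% |

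Adjusted null rejection stays near 5%. Mean 95% CI half-widths for the paired t-test are 0.330, 0.346 and 0.391 at k = 0.2, 0.3 and 0.5, against 0.318 adjusted: 4%, 9% and 23% wider.

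**Step 4, chance imbalance.** If L subjects are lost at random after balanced assignment, leaving 40, the mean visit-position difference has SD √[(2/40) × L/(39 + L)]:
- L = 5: √(0.05 × 5/44) = 0.08 visits
- L = 10: √(0.05 × 10/49) = 0.10 visits
- L = 20: √(0.05 × 20/59) = 0.13 visits

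Multiplied by 1.96 × 0.3, the 95% range of chance bias at k = 0.3 is about ±0.04, ±0.06 and ±0.08 SD, zero on average.

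**The case against.** The strongest reply is that the plan already deals with order, by design. Counterbalancing makes the unadjusted paired comparison valid, and the authors flag order as a problem only where counterbalancing is absent. This stands. A reader might infer from the missing visit term that H3.1 and H3.2 are biased or prone to false positives. The documents do not support that: with balanced orders the error is in the conservative direction.

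Second, the size rests wholly on an assumed trend. Subjects practise the task in the mock scanner (Section 6.2.1) and do the full n-back scan at visit 2, before any analysed visit, so much of the learning may be over. A linear k of 0.3, where the loss reaches about 5 points, means a gain of 0.6 SD from visit 3 to visit 5, more than the 0.454 SD effect itself. This also stands. It limits the likely benefit but does not remove the case for a term that costs almost nothing.

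Third, it is tempting to assume that all 20 spare recruits are lost after their order is set. The documents do not say so. They do not state when order is assigned, and the tolerability rule operates at visit 2: "If a subject cannot tolerate iTBS, they will be withdrawn from the protocol". Hence the range of 5, 10 and 20 losses.

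Fourth, the planned imaging tests also lack a visit term, and a reader might carry these figures over to them. Nothing here quantifies a visit effect on activation, connectivity or perfusion, so the point is confined to Aim 3.

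Finally, Section 8.0 lets implementation differ slightly from the text. That would permit a visit term but does not pre-specify one, and a choice made after seeing the data is what a plan should avoid.

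**Conclusion.** The point holds for Aim 3 as a low-cost refinement, not as a threat to validity. If 2-back accuracy has a common trend over visits 3 to 5, the paired t-tests overstate their standard error. Under the stated assumptions the loss of power is about 2 to 3 points at k = 0.2, 5 at k = 0.3 and 15 at k = 0.5 for a linear trend, and at most about 5 points up to k = 0.5 if learning stops after visit 4. With no trend nothing is lost by the present plan. Chance imbalance after losses adds a small error, zero on average. The direction of the effect follows from the design. Its size cannot be fixed from the documents and may well be small.

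**What to change.** Replace the post-hoc paired t-tests with wording such as:

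> H3.1 and H3.2 will be tested on the within-subject difference between the two conditions, adjusted for the visit positions (3, 4 or 5, categorical) of the two sessions, with the intercept as the condition effect. The three-condition model will likewise include categorical visit: a mixed model with condition, visit, sex and age and an unstructured within-subject covariance.

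For the differences, use one covariate for visit 4 and one for visit 5. Each is the indicator for the first condition minus the indicator for the second, not centred. Apply the same to d-prime and reaction time. Report the estimated visit effects and the number analysed per order.

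The cost is SAP wording and 2 degrees of freedom (39 to 37; critical t from 2.023 to 2.026). With no trend, simulated power goes from 80.2% to 79.9% with near-balanced orders, and from 80.2% to 79.3% if a random 40 of 60 balanced orders remain. No new data are needed, since each subject's visit order is known.

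The term does not remove differences between subjects in learning rate, or the extra 2-back done during stimulation in one condition (Section 6.3.3).
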